### **HRCT Scans**

HRCT scans obtained within 4 months before the Screening period as part of the standard of care for a patient may be used to confirm eligibility, provided they meet all of the image acquisition and quality criteria required by the CT expert readers. All HRCT digital images are to be stored on a dedicated disk. The images will be anonymized using a tool developed by the Quantitative Imaging Laboratory at National Jewish Health. The Quantitative Imaging Laboratory will be tasked with interpretation, archiving, and quantitative analysis of the images. One thoracic radiologist with expertise in FHP will review the HRCT scans using an electronic score sheet. Data regarding the HRCT interpretation will be entered electronically

into the trial research's database and incorporated into the clinical database. Evidence of progression, stability, or improvement in fibrosis on temporally blinded visual comparison of baseline and week 52 HRCT scans will be documented on a five-point scale (much better, better, same, worse, and much worse).

### **Pathology**

For patients with surgical lung biopsies or bronchoscopic biopsies, a score sheet will be used to assess whether or not the biopsy is consistent with a diagnosis of hypersensitivity pneumonia and to record the associated histologic findings. One thoracic pathologists will score each biopsy. If a patient will be excluded from the study based on the pathology assessment by a single reader, a second reader will be used to resolve the discrepancy. The microscopic features section of the score sheet will be recorded for each read and since they represent semi-quantitative data, the mean will be used as the overall result for later analysis. The microscopic section of the score sheet will not be used to determine subject inclusion/exclusion.

**Score sheet:**

Biopsy type: Bronchoscopic, Wedge

#### Diagnosis:

Is the biopsy consistent with a pathologic diagnosis of hypersensitivity pneumonia:

If the biopsy is inconsistent, what is your overall diagnosis?

#### Microscopic findings:

Please assess the extent of each of the following on a scale 0-3 (0 = none, 1 = mild/rare, 2 = moderate, 3 = severe/extensive)

Airway-centered chronic inflammation:

Nonnecrotizing granulomas:

Multinucleated giant cells:

Peribronchiolar metaplasia:

Organizing pneumonia:

Fibrosis:

Microscopic honeycombing:

### **Spirometry and DLCO Measurements**

All equipment, procedures, and personnel qualifications for the assessment of lung function are based on the recommendations of the American Thoracic Society:

1. Spirometry measurements will include FVC and FEV1
2. DLCO will be measured by determining the diffusing/transfer capacity of the lung for carbon monoxide.

Data for FVC, DLCO will be entered electronically blindly into the research's database and incorporated into the research electronic data capture (REDCap).

### **6-Minute Walk Test (6MWT) and Borg Scale**

The 6MWT measures the distance that a patient can walk at his/her own pace on a measured, flat hard surface in a period of 6 min. The 6MWT assesses the global and integrated responses of all body systems involved during walking. The 6MWT will be performed based on ERS/ATS recommendations. The Borg Scale is an instrument to be self-administered by the patient as part of the 6MWT procedure.

### **St George's Respiratory Questionnaire (SGRQ)**

The SGRQ is patient-self-administered questionnaire to measure and quantify health-related health status. It has been shown to correlate well with established measures of symptom level, disease activity and disability.

### **A Tool to Assess Quality of life in (L-IPF)**

The L-IPF is patient-self-administered questionnaire to measure and quantify health-related health status developed at National Jewish Health.

### **UCSD Shortness of Breath Questionnaire**

The UCSD SOBQ is a symptom-specific, 24-item, patient-self-administered questionnaire that will be used to assess shortness of breath on the study subjects while doing a variety of activities of daily living.

### **Physical Exam and Vital Signs**

A complete physical examination will be performed by a study physician and will include all body systems pertinent to the subject. If clinically significant abnormalities are observed before Day 1, they will be reported in the patient's medical history. If clinically significant abnormalities are observed after Day 1, the investigator will decide if they are new adverse events. Vital signs for this study protocol include heart rate, blood pressure, oxygen saturation and FiO2.

### **Electrocardiograms (ECGs)**

During the study, if the QTc interval is >550 msec. and verified by the study site or local cardiologist, study drug will be stopped. If the QTc interval is between 500 and 550 msec. and verified by a study site study treatment will be interrupted. ECG data will be incorporated into the clinical database.

### **Directed History During the Study**

The following will be assessed as directed history:

- Clinical and exposure history.
- AEs/SAEs.
- Concomitant medications.

- Dosing and compliance.
- Supplemental oxygen use.
- Hospitalizations.

### **Vital Status Assessments**

Vital status will be assessed for those who are no longer able to participate in the study procedures (Early Withdrawal from Study Procedures) at protocol-specified time points (study visit dates) until the Follow-Up Visit. Subjects who undergo lung transplantation or who chose to withdraw from study procedures early will be followed for vital status until Week 52. This assessment will most likely be accomplished remotely (i.e., via telephone or electronically). These communications are well documented in the participants study file. Vital status procedures are as follows:

1. If the subject is not available, an authorized family member or representative will be contacted by telephone or electronically at the milestones of study visit dates.
2. In the case of lung transplant, the date of the transplant, details of the transplant, dates of hospitalization, and the current vital status will be obtained.
3. In the case of a subject death, the date, details, and cause of death will be requested from the subject's representative or family member.
4. If a subject is lost to follow-up, vital status will be ascertained through the use of death registries.

### **Mortality Assessment**

Mortality Assessment will be closely examined by [name] including the details and the relationship to FHP for each death. Documentation regarding deaths must be requested and should include (but is not limited to) discharge summaries, death certificates, and autopsy reports.

### **Washout and Screening Periods**

Written informed consent will be obtained before initiating any study-associated procedures or changes to a pre-existing treatment regimen for purposes of this study. Procedures conducted during Screening will be used to determine the eligibility of each patient for study inclusion before randomization and to establish subject Baseline status. If subjects fail Screening due to a condition that subsequently resolves (e.g., infection), they may be considered for rescreening.

### **Washout Period (28 Days)**

Before entering a subject in the Washout Period, all relevant medical history, diagnostic findings, and measures of disease severity should be reviewed to evaluate the subject's suitability for the study. Written informed consent must be obtained before withdrawing or tapering the subject off prohibited therapies. The study team must explain to the subject that entry into the study is not guaranteed. Any subject identified for the study must

discontinue all prohibited medications at least 28 days before Screening. This is the Washout Period. If a medication must be tapered, tapering must start early enough that the subject has discontinued the drug 28 days before the start of Screening.

### **Screening Period**

The Screening period is defined as the time between the date of the first Screening procedure and may last up to 30 days. Screening procedures may be conducted on different days within the Screening period if convenient.

The following procedures will be performed during Screening:

1. Written informed consent, if not already obtained during the Washout Period.
2. Complete medical history, review of systems, and review of concomitant medications.
3. Physical examination, vital signs, weight, and height.
4. Clinical laboratory assessments, including hematology, serum chemistries, serologic tests clinically within the past 30 days, and pregnancy test for women of childbearing capacity.
5. ECG.
6. Resting Oxygen and FIO2.
7. A 6MWT with Borg Scale pre and post.
8. Transfer of all surgical lung biopsies, if available, for evaluation by pathologist.
9. Review of transbronchial biopsy and/or BAL, if available, to assess eligibility
10. HRCT within the past 4 months, spirometry and DLCO within the past 30 days to assess eligibility.

### **Assessments during Treatment**

#### **Eligibility and Randomization (Day 1)**

All Day 1 procedures must be performed before randomization and before administration of study treatment. This study has no Day 0. Randomization (Day 1) will occur no more than 30 days after the start of the Screening period, and study treatment will begin on the day of randomization. Once the patient is confirmed to be eligible for randomization, the patient will be randomized at the end of Day 1.

The following procedures will be performed on Day 1:

#### **Before Randomization**

1. Directed history (including review of AEs/SAEs, concomitant medications, oxygen use, and hospitalizations).
2. Physical examination, vital signs, FiO2 and weight.
3. Clinical laboratory assessments, including hematology, serum chemistries, pregnancy test for women of childbearing capacity.
4. Spirometry (FVC, FEV1) and DLCO.
5. 6MWT with Borg Scale pre and post.

6. UCSD SOBQ, L-IPF and SGRQ.
7. Confirmation of patient eligibility for study participation.
8. Genetic testing (RNA-seq and ChIP-seq).

#### **Randomization**

9. All unidentifiable randomization codes will be generated by a statistician independent of the trial conduct. All subjects, monitors, and study center personnel related to the study, including the site pharmacist will be blinded to study treatment throughout the study. The randomization schema will be securely maintained electronically at the NJH Clinical Research Unit.

#### **After Randomization**

10. Instruct the subject on how to titrate the dose of study treatment.
11. Dispense 13-week supply of study treatment. Dosing should start on the day of randomization (see clinical IB section 3).
12. Dispense subject diary and instruct on its use.

#### **Week 1 Telephone Assessment ( $\pm$ 2 days)**

A telephone interview will be conducted to determine vital status and to assess tolerability of study treatment, subject compliance with dosing, and titration of study treatment.

#### **Week 3 ( $\pm$ 2 days)**

The following will be performed at Week 3:

1. On-site safety assessment.
2. Clinical laboratory assessments including comprehensive metabolic panel.

#### **Week 5 ( $\pm$ 1 week)**

The following procedures will be performed at Week 5:

1. Directed history (including review of AEs/SAEs, concomitant medications, oxygen use, hospitalizations, dosing, and diary).
2. Physical examination, vital signs, FiO2 and weight.
3. ECG.
4. Clinical laboratory assessments, including hematology, serum chemistries, and pregnancy test for women of childbearing capacity.
5. Vital Status Assessment.

#### **Week 13 ( $\pm$ 2 weeks)**

The following will be performed at Week 13:

1. Directed history (including review of AEs/SAEs, concomitant medications, oxygen use, hospitalizations, dosing, and diary).
2. Physical examination, vital signs, FiO2 and weight.

3. ECG.
4. Spirometry (FVC, FEV1).
5. Clinical laboratory assessments, including hematology, serum chemistries, pregnancy test for women of childbearing capacity.
6. 6MWT with Borg Scale pre and post.
7. UCSD SOBQ, L-IPF and SGRQ.
8. Collection of any unused study treatment, review compliance and dispensing of 13-week supply of study treatment.
9. Dispense new diary, if required.
10. Vital Status Assessment.

#### **Week 26 (± 2 weeks)**

The following will be performed at Week 26:

1. Directed history (including review of AEs/SAEs, concomitant medications, oxygen use, hospitalizations, dosing, and diary).
2. Physical examination, vital signs, FiO2 and weight
3. ECG.
4. Spirometry (FVC, FEV1)/DLCO.
5. Clinical laboratory assessments, including hematology, serum chemistries, pregnancy test for women of childbearing capacity.
6. 6MWT with Borg Scale pre and post.
7. UCSD SOBQ, L-IPF and SGRQ.
8. Collection of any unused study treatment, review compliance and dispensing of 13-week supply of study treatment.
9. Dispense new diary, if required.
10. Vital Status Assessment.

#### **Week 39 (± 2 weeks)**

The following will be performed at Week 39:

1. Directed history (including review of AEs/SAEs, concomitant medications, oxygen use, hospitalizations, dosing, and diary).
2. Physical examination, vital signs, FiO2 and weight
3. ECG.
4. Spirometry (FVC, FEV1).
5. Clinical laboratory assessments, including hematology, serum chemistries, pregnancy test for women of childbearing capacity.
6. 6MWT with Borg Scale pre and post.
7. UCSD SOBQ, L-IPF and SGRQ.
8. Collection of any unused study treatment, review compliance and dispensing of 13-week supply of study treatment.
9. Dispense new diary, if required.

10. Vital Status Assessment.

**Follow-up Visit (+ 7 days)**

Patients who discontinue study treatment early will be required to return for a Follow-up Visit 28 to 35 days after their last dose of study treatment in this study. The following procedures will be performed at the Follow-up Visit:

1. Directed medical history (including review of AEs/SAEs, concomitant medications, oxygen use, hospitalizations, dosing, and diary).
2. Physical examination, vital signs, and weight.
3. Clinical laboratory assessments, including hematology, serum chemistries, pregnancy test for women of childbearing capacity.
4. Collection of diary.
5. Vital Status Assessment.

**Early Discontinuation of Study Treatment**

Subjects who discontinue study treatment before Week 52 will complete a Follow-up Visit. In addition to the procedures listed above for the Follow-up Visit, subjects who discontinue study treatment before Week 52 must return all used and unused study treatment. Subjects who discontinue study treatment will be asked to continue to complete all scheduled study assessments and procedures through Week 52.

### **Early Withdrawal from Study Procedures**

Subjects who withdraw from study procedures early for reasons other than withdrawal of consent will cease study procedures but should be reminded that they gave permission for Vital Status Assessments when they consented to participate in the study. Consent for Vital Status Assessments remains intact when a subject withdraws from study procedures. Such subjects will continue to complete Vital Status Assessments through Week 52. Subjects who withdraw consent in writing will cease all study procedures including vital status assessments.

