### *Key Secondary Efficacy Outcome Variables*

1. Progression-free survival (PFS) defined as the time from study treatment randomization to the first occurrence of any of the following events:
  - a. Relative decline from baseline in  $\geq 10\%$  in FVC and/or DLCO
  - b. Acute exacerbation of FHP defined as acute respiratory declined leading to hospitalization or ER or Urgent care evaluation; or evidence of all of the following criteria within a 4-week period in the outpatient setting:
    - i. Increase from baseline  $\text{FIO}_2 \geq 1 \text{ L O}_2$ .
    - ii. Clinically significant worsening of dyspnea and/or cough.
    - iii. New, superimposed ground-glass opacities or consolidation or new alveolar opacities on chest x-ray or CT.
    - iv. Primary: if all other causes excluded (e.g., acute gastro-esophageal aspiration, pneumothorax, infection, left heart failure, pulmonary

embolism, or identifiable cause of acute lung injury).

- c. A decrease from baseline of at least 50 meters in 6-minute walk distance.
- d. Change in background therapy (need for a new course of PO or IV steroids or for the patient receiving maintenance prednisone, as a need to increase the dose by 10 mg or more; and/or addition of cyclophosphamide, azathioprine, mycophenolate mofetil or mycophenolic acid).
- e. Death

2. Slope of FVC over 52-week treatment period.
3. Mean change in %DLCO at week 52
4. Proportion of patients with all-cause mortality.
5. Proportion of patients with all-cause hospitalization.
6. Proportion of patients with hospitalization for respiratory cause.
7. Proportion of patients with respiratory exacerbations requiring hospitalizations.
8. Proportion of patients with evidence of progression in fibrosis on visual comparison of baseline and week 52 HRCT scans.

*Exploratory Outcome Variables:*

1. Mean change from baseline in health-related quality of life, measured by St. George's Respiratory Questionnaire (SGRQ) (3 domain scores and total score), at Week 52.
2. Mean change from baseline in health-related quality of life, measured by A Tool to Assess Quality of Life Questionnaire (L-IPF) at Week 52.
3. Mean change from Baseline to Week 52 in dyspnea as measured by the University of California at San Diego Shortness-of-Breath Questionnaire (UCSD SOBQ) score.
4. Proportion of patients with evidence of progression, stability or improvement in fibrosis on texture-based quantitative analysis of CT.

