### **Key Secondary Efficacy Outcome Variables and Analyses**

Multiplicity adjustment will be performed across all secondary endpoints.

Progression-free survival will be compared between the pirfenidone 2403 mg/d and placebo groups using the log-rank test. A proportional hazards model will be used to estimate the hazard ratio. Descriptive analysis of progression free survival will be presented using Kaplan-Meier curves. Mortality will be analyzed using logistic regression with a treatment effect and accounting for potential over- or under-dispersion in the outcome.

The slope for annual rate of FVC decline will be analyzed using a random coefficient regression model with treatment and baseline FVC as covariates.

DLCO will be analyzed using a rank linear regression model with the rank change in %DLCO

from Baseline to Week 52 as the outcome variable and rank Baseline %DLCO and HP therapy as covariates.

Non-elective hospitalization from any cause and CT progression of fibrosis will be compared between the pirfenidone 2403 mg/d and placebo groups using logistic regression accounting for possible over- or under-dispersion in the outcome.

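### Subjects who leave study procedures but keep consent are still contacted through Week 52, yet those contacts do not collect hospitalizations, exacerbations or therapy changes, and no analysis rule covers the gap

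*Combined protocol and SAP*

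**What the plan says.** The section on early withdrawal from study procedures covers subjects who leave for reasons other than withdrawal of consent. These subjects "will cease study procedures but should be reminded that they gave permission for Vital Status Assessments when they consented", and one activity is kept: "Such subjects will continue to complete Vital Status Assessments through Week 52". The Vital Status Assessments section sets the timing, "at protocol-specified time points (study visit dates) until the Follow-Up Visit", and the mode: "This assessment will most likely be accomplished remotely (i.e., via telephone or electronically". (Its next sentence gives Week 52 as the end for subjects who withdraw from procedures or are transplanted.) The content listed there is vital status; the date, details and cause of any death; and, after a lung transplant, "the date of the transplant, details of the transplant, dates of hospitalization, and the current vital status will be obtained". No general question on hospitalization, exacerbation or background therapy appears.

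Key secondary endpoint 5 is "Proportion of patients with all-cause hospitalization". Endpoints 6 and 7 are proportions with respiratory hospitalization and with exacerbations needing hospitalization. PFS counts, among other events, acute exacerbations and changes in background therapy.

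For the analysis, the SAP text says "Non-elective hospitalization from any cause and CT progression of fibrosis will be compared" between arms by logistic regression. It gives no rule on length of follow-up or missing data, and names no separate analysis for endpoints 6 and 7. Multiple imputation is described only under the primary %FVC analysis. PFS is analysed by log-rank test and proportional hazards, with no stated censoring rule.

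**The concern.** The site has agreed access to these subjects up to Week 52 but does not ask about events that define four of the eight key secondary endpoints (1, 5, 6 and 7). Hospitalizations and medications are otherwise recorded in the directed history at clinic visits, which these subjects no longer attend. The intent-to-treat population keeps every randomized subject in the denominator, so an analyst must decide what an unobserved later period means, and the plan does not say.

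If unseen events were treated as no events, the arm with more early withdrawal would show fewer hospitalizations because it was observed for less time. For PFS, a subject who leaves because of worsening, and is censored on leaving, would make the censoring informative.

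**Working it through.** **1. Which routes could capture a later event?**

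- *Directed history at Weeks 5 to 52:* records hospitalizations and medications, but these are clinic visits that withdrawn subjects have stopped.
- *Follow-up Visit:* also reviews hospitalizations, but only once, 28 to 35 days after the last dose, and it is itself a visit with procedures.
- *Safety reporting:* under Adverse Event Reporting Period it closes at the earlier of 28 days after the last dose or study discontinuation. After that only SAEs attributed to study treatment are reported (also Post-Study Adverse Events).
- *Vital status contact:* continues to Week 52, but covers hospitalization only after transplant.

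A leaver admitted some months later for a reason not attributed to study drug is reached by none of these, unless transplanted or the admission emerges from details of a death.

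**2. How many subjects could be affected?** The plan's own figure reproduces: 38 evaluable / (1 − 0.10) = 42.2, against about 42 planned. The allowance is 42 − 38 = 4 subjects. At 2:1, 42 gives 28 on pirfenidone and 14 on placebo. Four is an upper guide, because attrition may also include deaths, transplants and written withdrawals of consent.

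**3. Effect on a proportion endpoint.** The documents give no event rate or withdrawal time, so these are assumptions: one-year risk p, equal in both arms; constant hazard; all four leavers on pirfenidone, leaving at fraction t of the year; unseen events counted as none.

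- Event-free when leaving: S = (1 − p)^t.
- Patients missed: m = 4 × [S − (1 − p)]. A leaver hospitalized before leaving is already counted.
- Observed pirfenidone proportion: q = (28p − m)/28.
- Odds ratio read under no true effect: [q/(1 − q)] / [p/(1 − p)].

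For p = 0.20 and t = 0.5: S = 0.8944; m = 4 × 0.0944 = 0.38; observed events 5.6 − 0.38 = 5.22; q = 0.1865; odds 0.229 against 0.25; odds ratio 0.92.

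| One-year risk | Exit | Patients missed | Null odds ratio reads |
|---|---|---|---|
| 10% | Week 13 | 0.30 | 0.88 |
| 10% | Week 26 | 0.20 | 0.92 |
| 20% | Week 13 | 0.58 | 0.87 |
| 20% | Week 26 | 0.38 | 0.92 |
| 40% | Week 13 | 1.12 | 0.84 |
| 40% | Week 26 | 0.70 | 0.90 |

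**4. Other allocations of the leavers** (same method, same risks and exit times). With 10% leaving in each arm, about 4 to 7% of events are lost and the null odds ratio stays at 1.0. With 7.5% leaving on pirfenidone and 15% on placebo, it reads 1.04 to 1.10.

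**5. Uncertainty without assumptions on risk.** If all four leavers are in one arm and their outcomes are unknown, the gap between best and worst case is 4/28 = 14.3 points on pirfenidone or 4/14 = 28.6 points on placebo.

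**The case against.** The strongest reply is that the protocol already protects the main group at risk. Intolerance leads first to stopping study drug, and subjects who only stop drug are asked to complete all assessments through Week 52 (Study design; both sections on early discontinuation of study treatment) and to attend the Follow-up Visit. Only those who also stop visits but keep consent are affected. This stands, and it is why the group is small.

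The shift is also small beside sampling error. With 5.6 of 28 and 2.8 of 14 expected events, SE(log OR) = √(1/5.6 + 1/22.4 + 1/2.8 + 1/11.2) = 0.82, so the 95% limits lie a factor of e^(1.96 × 0.82), about 5, either side. This stands too.

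Some stronger readings are tempting, but the documents do not support them:

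- *Leavers are counted as not hospitalized, and PFS is censored at withdrawal.* Neither is written; the plan is silent, and leavers could equally be treated as missing.
- *The contact asks only whether the subject is alive.* Death and transplant details are also collected.
- *Therapy changes and outpatient exacerbations are lost to a simple proportion.* They feed only PFS, a time-to-event endpoint.
- *The bias favours pirfenidone.* That depends on which arm loses more subjects, which the documents do not predict.
- *Sicker leavers would pull the observed odds ratio lower still.* Unseen events cannot change the observed count. If the hazard doubles after Week 26 (p = 0.20), 4 × 0.8944 × 0.20 = 0.72 patients are missed, but 5.22 are still observed and the odds ratio still reads 0.92. What moves is the true total, to 5.22 + 0.72 = 5.94.

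**Conclusion.** The point holds as a gap in data collection with no analysis rule behind it. For subjects who leave procedures but keep consent, the documents provide contact to Week 52 without asking about events that endpoints 1 and 5 to 7 need. Exceptions are SAEs attributed to study drug and hospitalization dates after transplant.

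The size is modest: at most about 4 of 42 subjects, with a null odds ratio of about 0.84 to 0.92 even if all of them are on pirfenidone. That range rests on assumed risks of 10 to 40%, exit at Week 13 or 26, and unseen events read as none. The case for acting is not a large expected bias. It is that the loss can be avoided at little cost during the trial and is hard to repair or measure afterwards.

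**What to change.** **Data collection.** In Vital Status Assessments and Early Withdrawal from Study Procedures, extend the existing contact, for all withdrawn subjects who keep consent, to record:

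- any hospitalization: date, cause, elective or not, respiratory or not;
- any ER or urgent-care visit for acute respiratory decline;
- any new or increased FHP therapy.

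Make sure the consent wording covers these questions; the consent pages were not available, so it may already do so. Give one end date for the contacts, since Vital Status Assessments names both the Follow-Up Visit and Week 52.

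**Analysis.** In Key Secondary Efficacy Outcome Variables and Analyses, say that subjects with incomplete follow-up are not counted as event-free by default. State a missing-data rule for endpoints 5 to 7, or add a supportive time-to-first-hospitalization analysis censored at last contact. State the PFS censoring rule. Censoring at last contact can still be informative, so the added questions matter more than the choice of model.

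**Cost.** A few questions in contacts already planned, possibly a consent amendment, and a short addition to the analysis text; no change in sample size. The information would be remote self-report, some subjects may decline the extra questions, and those who withdraw consent in writing remain out of reach.
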